Treatment of Medial Tibial Stress Syndrome using an Investigational Lower Leg Device. A Randomised Controlled Trial.

[figure not shown]
Version Number: 11

Date of Protocol: 13/2/2017

Declaration of the Principal Investigator: I have read and understood the protocol document and agree to conduct the study as outline in the protocol and also in accordance with Australia Research Guidelines.

NAME OF PRINCIPAL INVESTIGATOR: [name]

SIGNATURE OF PRINCIPAL INVESTIGATOR:

DATE:13/2/17

SYNOPSIS

Treatment of Medial Tibial Stress Syndrome using an Investigational Lower Leg Device. A Randomised Controlled Trial.

Protocol version: 4

LIST OF INVESTIGATORS

Principal Investigator: [name]
Orthopaedic Research Institute
[name]
St George Hospital
[name]
[name]
[contact]
[contact]
Email: [contact]

Co Investigator: [name]
Orthopaedic Research Institute
[name]
St George Hospital
[name]
[name]
[contact]
[contact]
Email: [contact]

Co Investigator: [name]
Sydney Sports Medicine Centre
[name]
[name]
Sydney Olympic Park
[contact]
[contact]
Email:

Co Investigator: [name]
Orthopaedic Research Institute
[name]
St George Hospital
[name]
[name]
[contact]
[contact]
Email: [contact]

TREATMENT OF MEDIAL TIBIAL STRESS SYNDROME USING AN INVESTIGATIONAL LOWER LEG DEVICE. A RANDOMISED CONTROLLED TRIAL. VERSION 11 (13/2/17).

2

Summary

Study title:	Treatment of Medial Tibial Stress Syndrome using an investigational Lower Leg Device. A Randomised Controlled Trial.
Protocol version	1
Objectives	
Primary objective: Return to full-time sport/activity levels and recurrence of MTSS after return to full-time sport.
 
Secondary objectives: Level of shin pain during rest, with ADLs and during rehabilitation running each week prior to return to activity, time to progress through each stage of the rehabilitation protocol prior to return to full activity, bilateral active dorsiflexion range of motion at initial assessment, at return to full-time activities and at 6 weeks, 3 months and 6 months after return to full-time activities, compliance with device use and overall patient satisfaction with the device.

Study design	Prospective, double-blinded, randomised controlled trial
Planned sample size	50
Selection criteria	Symptomatic medial tibial stress syndrome of at least 6 weeks duration diagnosed on the basis of history of diffuse, dull lower leg pain with activity, and palpable tenderness of the posteromedial tibial border.
Study procedure	Patients randomized to one of two groups to receive either the novel device or a placebo to be worn on the lower leg, first fitted at initial visit. They will then undergo a home rehabilitation program and be followed up at 6 weeks, 3 months, and 6 months in the clinic.
Statistical considerations	
Sample size 50
 
Statistical analysis will be performed using SigmaPlot v11 (Systat Software, Inc. Chicago, IL,USA).

Duration of the Study	8 month follow up

Table of Contents

1. BACKGROUND	5
1.1. Disease Background*.....	5
1.2. Rationale for Performing the Study*.....	7
2. STUDY OBJECTIVES*	7
2.1. Primary Objective*	7
2.2. Secondary objectives.....	7
3. STUDY Design*	8
3.1. Design*	8
3.2. Study Groups	8
3.3. number of participants*	8
3.4. number of centres	8
3.5. duration	8
4. Participant section	8
4.1. Inclusion Criteria*	8
4.2. Exclusion Criteria*	8
5. STUDY Outline*	9
5.1. Study Flow Chart	9
5.2. Investigation plan*	9
5.3. Study Procedure Risks*	11
5.4. Recruitment and Screening*	11
5.5. Informed Consent Process*	12
5.6. Enrolment Procedure*	12
5.7. Randomisation Procedure.....	12
6. SAFETY*	12
6.1. Adverse Event Reporting*	12
7. BLINDING AND UNBLINDING	12
8. STATISTICAL CONSIDERATIONS*	12
9. STORAGE AND ARCHIVING OF STUDY DOCUMENTS*	13
10. Ethical considerations	13
11. Financing and Insurance	14
12. Publication policy	14
13. REFERENCES*	14
14. Appendix 1: Modified bruce protocol	17
15. Appendix 2: Participant Questionnaire	18

1. BACKGROUND

1.1. DISEASE BACKGROUND*

Shin splints, also known as Medial Tibial Stress Syndrome (MTSS), is an overuse injury or repetitive-stress injury of the shin area. A range of stress reactions of the tibia and surrounding musculature occur when the body is unable to heal properly in response to repetitive muscle contractions and tibial strain¹⁴.

MTSS occurs in approximately 4-20% of the general population¹⁴ and has significantly increased prevalence (35%) in athletes, particularly runners, and military personnel¹³.

The most common complaint is vague, diffuse pain of the lower extremity along the medial distal tibia and is associated with exertion^{1,5}. Clinical examination of the distal one-third of the medial border of the tibia often reveals tenderness to palpation with the anterior tibia often being non-tender¹³. Patients with early phase MTSS experience the worst pain at the beginning of exercise and this gradually subsides during training or within minutes of cessation of exercise. As the disease progresses the pain presents with less activity and may occur at rest¹³.

There are multiple risk factors for developing MTSS, however, muscle imbalance and inflexibility, especially tightness of the triceps surae (gastrocnemius, soleus, and plantaris muscles) has been documented heavily in the literature as being commonly associated with MTSS^{1,6,7}.

The pathophysiology is not well understood, however, it is believed to be a combination of tendinopathy, periostitis, periosteal remodelling, and stress reaction of the tibia¹⁻³. Dysfunction of the tibialis posterior, tibialis anterior, and soleus muscles are also common implicated^{1,2,3}. These various tibial stress injuries appear to be caused by alterations in tibial loading, as chronic, repetitive loads cause abnormal strain and bending of the tibia¹. Studies have attributed the pain experienced in MTSS to the disruption of Sharpey fibers that are connected to the medial soleus fascia and run through the periosteum of the tibia to insert into the bone²². Interestingly, in patients with chronic MTSS radiography has shown periosteal involvement including periosteal exostoses¹³. Periosteal oedema and subsequent bone marrow oedema into the periosteum has also been shown as a significant feature of chronic MTSS³.

There is also discussion that MTSS, as a result of calf tightening, may be associated with a myofascial pain disorder which is 'composed of hypercontracted extrafusal muscle fibres' characterised by the presence of tender, firm nodules called trigger points²¹. These nodules are hyperirritable upon palpation. One recommended treatment for myofascial pain disorder is mechanotherapy²⁰ to provide acute

symptomatic treatment and allow for more rapid commencement of an appropriate rehabilitation program.

In concordance with both bone loading and myofascial pain theories, other studies have suggested that MTSS develops as a result of repetitive impact forces that eccentrically fatigue the soleus leading to tibial bending or bowing and overloading the capacity for bone remodelling^{1, 12}.

Treatment is predominantly conservative (rest, ice, analgesia, stretching, massage), however, few advances have been made in the treatment of MTSS over the last few decades¹³. Current treatments are mostly based on expert opinion and clinical experience with few well-conducted randomised control trials (RCT)⁴. Rest has been shown to be the single most important treatment in acute MTSS^{1,3,7,12}. For many athletes, however, prolonged rest is not ideal.

Other treatments include use of NSAIDs for analgesia along with ice for ~15-20mins in the acute phase¹³. Physiotherapy has been shown to be helpful (ultrasound, whirlpool baths, phonophoresis, soft tissue mobilisation, electrical stimulation, and unweighted ambulation have been shown to be effective in the acute setting)^{1,3,5-7,9,12}. However, many athletes require more regular treatment that suggests a more athlete self-directed method of treatment could be helpful in the setting of MTSS.

Similarly, a regular program of stretching and strengthening exercises has been shown to be effective in prevention of, and in the rehabilitation period following, MTSS^{1,3,5-7,9,12}.

Appropriate footwear and orthotics has been shown to reduce the incidence of MTSS^{1,3,4-8,12} and can prevent repeat episodes^{1,4}. Shock-absorbing insoles have shown potential in prevention and treatment of MTSS in a military population, however, with unclear results due to methodological flaws²³. Finally, a systematic review has highlighted that correction of musculoskeletal dysfunctions can improve pain and overall function and may be helpful in preventing recurrence¹³.

Some studies have introduced a lower limb brace designed to treat MTSS, with particular focus on a military population^{16,19}. However, statistical significant results were not demonstrated between experimental and control groups. This has been attributed to methodological limitations such as a small sample size ($n < 25$), compliance issues, non-validated outcome measures, and a short time period for evaluation of efficacy¹⁷.

Despite previous studies showing little efficacy of a lower limb brace for the treatment of MTSS, this simple and patient self-directed option should not be disregarded for its potential role in mechanotherapy²⁰. With a carefully constructed study

methodology, appropriate sample size, using newly developed evaluation tools not previously available for use in clinical settings¹⁸, over a longer period of time compared to previous brace studies we believe a more clinically relevant picture of the role of lower limb braces in the treatment of MTSS may be realised.

As agreed upon by a large body of evidence, the key to treatment of MTSS is prevention¹, however, to date, there is limited evidence to support our current treatment and interventions for MTSS⁴.

The current literature regarding MTSS clearly demonstrates a multifaceted syndrome in its etiology and associations. To improve our current treatment, therefore, requires a multifaceted approach that addresses both bone loading and myofascial aspects of the condition.

1.2. RATIONALE FOR PERFORMING THE STUDY*

The proposed study is designed to determine whether current treatment methods with an adjuvant novel device for medial tibial stress syndrome are more effective than the current treatment methods without the novel device. Rest is currently the most effective treatment modality, however, many active individuals find this period of rest frustrating and detrimental to their goals, particularly amongst those competing in high level sport. The aim of the device is to reduce the amount of rest required to return to previous activity levels whilst also symptomatically treating the pain associated with medial tibial stress syndrome.

It is expected that we should be able to show a treatment effect of the device in terms of time taken to return to full activity load, recurrences after return to full activity load and overall shin pain. This will be compared to that of the placebo group to see if the device provides any additional treatment effect beyond that of the placebo group.

2. STUDY OBJECTIVES*

2.1. PRIMARY OBJECTIVE*

Time to return to full-time sporting activities, and recurrence of symptoms after return to full-time activities.

2.2. SECONDARY OBJECTIVES

Level of shin pain during rest, with ADLs and during rehabilitation running each week prior to return to activity, time to progress through each stage of the rehabilitation protocol prior to return to full activity, bilateral active dorsiflexion range of motion at initial assessment, at return to full-time activities and at 6 weeks, 3 months and 6 months after return to full-time activities, compliance with device use and overall patient satisfaction with the device.

3. STUDY DESIGN*

3.1. DESIGN*

- Prospective, double-blinded, randomized controlled trial.

3.2. STUDY GROUPS

Normal Treatment with the Novel Device Group (Device group)

Normal Treatment with placebo Device Group (Placebo group)

3.3. NUMBER OF PARTICIPANTS*

50

3.4. NUMBER OF CENTRES

1

3.5. DURATION

- Start date May 2016, expected end date May 2020
- Expected time period for the recruitment phase of the study is 24 months

4. PARTICIPANT SECTION

4.1. INCLUSION CRITERIA*

- Symptomatic medial tibial stress syndrome of at least 6 weeks duration, diagnosed on the basis of:
 - History of diffuse, dull shin pain that is associated with exercise,
 - Palpable tenderness of the posteromedial tibial border

[figure not shown]
4.2. EXCLUSION CRITERIA*

- Diagnosis of stress fracture in the previous 6 months
- Clinical suspicion of a current stress fracture due to localised point tenderness on the anterior or medial border of the tibia unless ruled out by an MRI (MRI negative for bone stress reaction)
- Signs of plantar fasciitis including heel pain on first steps in the morning and tenderness to palpation over the posteromedial calcaneal tuberosity
- Previous diagnosis of compartment syndrome
- Suspicion of chronic exertional compartment syndrome on the basis of history of shin or calf pain brought on at a predictable point in activity, that worsens if exercise continues and is relieved by rest, unless excluded with compartment pressure testing
- Clinical signs of complex regional pain syndrome including pain out of proportion to the inciting event, allodynia, hyperalgesia, diffuse oedema, skin changes and difference in temperature between limbs
- Previous diagnosis of popliteal artery entrapment syndrome
- Clinical suspicion of popliteal artery entrapment syndrome based on disappearance of pedal pulses on repetitive plantarflexion
- Clinical suspicion of radicular leg pain including history of back pain associated with the leg pain and/or reproduction of leg pain on SLR testing with added dorsiflexion
- Neurological disease affecting the lower leg
- Coagulation disease
- Pregnancy

- Age less than 18
- Individuals with increased risk of fungal infection
- Individuals with disorders affecting the skin
- BMI > 35
- Any condition that increases risk of infection of the lower limb

5. STUDY OUTLINE*

5.1. STUDY FLOW CHART

5.2. INVESTIGATION PLAN*

List Interventions	Enrolment visit	Initial assessment	Assessment prior to	6 week follow up	3 month follow up	6 month follow up
--------------------	-----------------	--------------------	---------------------	------------------	-------------------	-------------------

TREATMENT OF MEDIAL TIBIAL STRESS SYNDROME USING AN INVESTIGATIONAL LOWER LEG DEVICE. A RANDOMISED CONTROLLED TRIAL. VERSION 11 (13/2/17).

9

		and fitting of device/placebo	return to sport			
Informed Consent	✓					
Inclusion / Exclusion criteria	✓					
Patient filled form - evaluation of shin pain and function (to be completed weekly)		✓	✓	✓	✓	✓
Physical examination		✓	✓	✓	✓	✓
Treadmill testing		✓	✓	✓	✓	✓
Adverse Event & Serious Adverse Event Assessment			✓	✓	✓	✓

At the enrolment visit, patients will be examined to determine a clinical diagnosis of MTSS according to the inclusion and exclusion criteria. Following confirmation of eligibility for enrolment in the study, patients will be asked to read a patient information sheet that outlines the purpose of the study and what is involved. They will then be given a consent form and asked to complete it if they wish to partake in the study.

Once informed consent is obtained, the patient's age, gender, occupation, duration of symptoms, leg(s) involved, highest level of sport achieved, and previous history of MTSS will be recorded.

Participants will be randomised to the novel device group or the placebo group. The novel device group will receive the Solushin (Solushin Pty Ltd, Australia), complete with compressive hemispheres and rod, fitted to the patient. The placebo group will receive a garment that appears to look the same as the Solushin, however, it will lack the functional elements of the device. If participants have bilateral MTSS they will be given the same device for both legs – that is, a participant randomized to the investigational device group with bilateral MTSS will receive one investigational device for each leg and vice versa.

All patients will be instructed on the correct application of the Solushin device or the placebo, respectively, with both groups being required to wear their device from commencement of the study up until 6 weeks after return to full-time activity. Patients will be instructed to wear their device for at least 2 hours prior to undergoing their return to full activity program and 2 hours after completing their activities. If patients do not participate in exercise in any day, they will be instructed to wear their device for at least 2hrs in the morning and 2hrs in the afternoon during those days.

Participants will be instructed by the clinician to follow a standardized return to full activity protocol with graded progression based on symptoms. They will be asked to refrain from any other running or load bearing activities other than activities of daily living and the rehabilitation exercises until return to full activity. They will be permitted to cycle, swim and participate in resistance programs should they choose to.

All participants will also have the option to undergo other treatment procedures such as ice, stretching, massage and soft tissue techniques recommended by their usual treating clinician.

Initial assessment of MTSS will require participants to perform an active range of dorsiflexion test followed by a treadmill running test whereby patients will be progressed through a modified Bruce protocol (Appendix 1) (see my note on appendix) and asked to stop at the point at which their leg pain is elicited. The end of the test will occur when they complete the protocol or when they reach their maximal heart rate ($220 - \text{age}$) if no symptoms occur. Patients will be asked to complete a VAS Score to rate their pain prior to, immediately after and 5 minutes after treadmill testing. The same assessments will be made at follow-up appointments in the clinic prior to return to full activity and again at 6 weeks, 3 months and 6 months after return to full load activities.

The nominated Medical Monitor is [name] who will follow up with any participants who are unhappy with their management or any other aspect of the trial. Participants will be able to contact [name] for review whether that is a medical review, a second diagnostic opinion or a conversational review about the conduct of the study. In addition the first 5 participants enrolled in the study will be closely monitored in the early stages of use of the device for adverse effects. This will be done via a clinical examination once a week for the first two weeks, then fortnightly for the next two fortnights for a clinical examination. Additionally, there will be a phone interview every two days for the first week prior to the in-person clinical examination allowing the investigators to identify and act on issues earlier than the one week visit.

Patients will be asked to complete a questionnaire and send it to the clinician once a week until return to full-time activity, then every fortnight for the duration of the study (Appendix 2).

The nominated Data Safety Monitoring Committee consists of [name] and [name] who will monitor safety during the trial via reviewing the results of the first 5 participants enrolled in the study and any other participants who report adverse events throughout the trial.

5.3. STUDY PROCEDURE RISKS*

The risks in this study are related to the device material. There is a low risk that the material in both the device group and the placebo group can promote fungal or bacterial colonization of the skin that is in direct contact with device. This risk is lowered by the use of an antifungal and antibacterial material that is machine washable. Due to the compressive nature of the device, there is a low risk that it will produce a tourniquet effect that could compromise haemodynamics and lead to formation of thromboemboli. However, the device is not designed to reach pressures consistent with tourniquets.

5.4. RECRUITMENT AND SCREENING*

Participants will be recruited via face to face discussion, sending of letters and/or flyers to Sydney physiotherapists, doctors as well as using social media platforms such as Facebook and Instagram.

Any patients who fit the inclusion criteria (identified from their initial history and clinic examination) will be considered as potential participants. Eligible patients will then be informed about the study and invited to attend a clinic appointment where they will be further examined to ensure they fit the inclusion criteria, don't meet any exclusion criteria and are willing to participate in the trial. Patients who fit the criteria will be given the PICF and given time to consider whether they would like to be a part of the study and if they are not sure we suggest that they go home to think about it and call to make another appointment if they wish to partake.

5.5 INFORMED CONSENT PROCESS*

The study will be explained verbally to the suitable participants and if they agree to participate they will be provided with a written explanation of the study and will fill out and sign a written informed consent form which will be put in their medical file.

5.6 ENROLMENT PROCEDURE*

If the participant meets inclusion criteria, has no exclusion criteria and agrees to participate in the trial they will be enrolled into the study after informed consent has been completed. The participant will receive a study enrolment number and this will be documented in the participant's medical record and on all study documents.

5.7 RANDOMISATION PROCEDURE

After enrollment participants will be randomized into one of two groups using a computer generated randomization code that will be held by an administrative staff member with no other involvement in the trial.

6. SAFETY*

6.1. ADVERSE EVENT REPORTING*

Adverse events will be assessed at each follow up and recorded in the participant's medical notes. We will also keep a log of all adverse events. We are considering adverse events to be any untoward medical occurrence in a participant which does not necessarily have a causal relationship with the study treatment. An adverse event can therefore be any unfavorable or unintended sign, symptom or condition and/or an observation that may or may not be related to the study treatment.

If participants feel that their shin pain has worsened, they will be re-evaluated at the 6 week follow-up visit for possible other causes of lower leg pain.

Participants are able to call or return to clinic at any time between the initial visit and the prior to return to sport visit. They have the option of obtaining an external second opinion of their condition at any time and proceeding with any other recommended treatment. Any other treatment received will be recorded at each subsequent visit.

All adverse events will be recorded in a case report form. It will not be reported to the ethics review committee immediately unless it impacts on the research and action is planned.

All serious adverse events will be recorded and reported individually to HREC if the information materially impacts the continued ethical acceptability of the trial or indicates a need for change to the trial protocol, otherwise they will be included in the annual Serious Adverse Events Summary Report.

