The study is designed to minimize potential detrimental effects of the researcher-participant relationship by making sure the researchers are not involved with the treatment of the patient outside of the study parameters and within the study participants are asked that they report any difficulties, complaints or adverse events to the researchers so that participants can be assessed immediately followed by the appropriate course of action.

Potential participants who are already involved in a separate study will be advised to remain in that study as a participant and not engage in another.

Researchers will minimize any dependency of participants by following the strict study protocol and instructing participants to do the same. Realistic participant explanations will be ensured through provision of the patient information sheet and consent form. Persons who decline participation or withdraw from the study will not be denied any treatment or be disadvantaged in any way.

Throughout the study, participants will be treated with respect, consent will be sought by an investigator who has no pre-existing relationship with potential participants and all information will be kept confidential as per section 9 of this protocol.

This protocol has been reviewed by Bellberry Human Research Ethics.

11.FINANCING AND INSURANCE

The researchers will conduct the study voluntarily in their free time. The experimental devices and placebo will be provided by Solushin Pty Ltd for no fee. Participants will be allowed to keep their device after completion of the study if they so wish. All clinicians (principal researcher and first author) have medical indemnity insurance that encompasses clinical trials.

12.PUBLICATION POLICY

Participants will be provided with a patient information and consent form which outlines the purpose of the study and the methodology, informing them that their information will be kept confidential, they may receive a placebo device and they have the right to withdraw from the study at any time. The plan for the study is to improve the management of medial tibial stress syndrome. Therefore, on completion the study will be submitted to publication to an appropriate peer-reviewed journal.

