16. APPENDIX 3: RETURN TO FULL ACTIVITY PROGRAM

- **Patients can progress each stage every 3 days if no pain with or following activity. No more than 2 running days in a row (i.e. one rest day out of every three)**
- **If experiences pain during or after activity or at rest – must have relative rest for 24 hours and continue with flow chart from one step back.**
- **Lack of progression or regression on flow chart will need medical review by trial doctor(s).**
- **Present for return to full training/sport assessment when completed flow chart pain free. Absolute minimum time is 33 days.**

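### Worsening shin pain is sent to a visit that non-recoverers never reach, and every adverse event assessment scheduled for all participants depends on finishing rehabilitation pain free

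*Protocol*

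**What the plan says.** On worsening pain, the protocol gives several responses:

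- Section 6.1: participants who feel worse are told that "they will be re-evaluated at the 6 week follow-up visit for possible other causes of lower leg pain". The sentence does not say which period of the trial it covers.
- Section 5.2 dates that visit. Assessments are made before return to full activity and "again at 6 weeks, 3 months and 6 months after return to full load activities". Section 2.2 uses the same origin. The synopsis lists the 6-week, 3-month and 6-month visits without naming one.
- Section 10: difficulties, complaints and adverse events are to be reported so that "participants can be assessed immediately followed by the appropriate course of action".
- Appendix 3: "Lack of progression or regression on flow chart will need medical review by trial doctor(s".
- Section 6.1, next paragraph: between the initial visit and the pre-return visit, participants may telephone or come back whenever they wish.

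On adverse events, section 6.1 states: "Adverse events will be assessed at each follow up and recorded in the participant's medical notes". In the section 5.2 table, the row "Adverse Event & Serious Adverse Event Assessment" has four ticks: the pre-return assessment, 6 weeks, 3 months and 6 months. The enrolment and fitting columns are empty. Appendix 3 lets a participant present for the pre-return assessment only once the flow chart has been finished without pain, and adds: "Absolute minimum time is 33 days".

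Section 5.2 makes one scheduled exception: "the first 5 participants enrolled in the study will be closely monitored in the early stages of use of the device for adverse effects". It also provides a questionnaire (Appendix 2), weekly until return and fortnightly afterwards. Section 5.3 names fungal or bacterial colonisation of the skin and thromboemboli as low risks.

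**The concern.** Two things go wrong if the plan is followed as written.

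First, site staff have inconsistent instructions for the same event. A participant whose pain worsens during rehabilitation is directed by one sentence to a visit that lies beyond the end of rehabilitation, and by other text to much earlier assessment.

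Second, scheduled collection of harms is conditional on recovery, which is tied to the primary outcome. Section 5.2 has the device worn from the start of the study until 6 weeks after return to full activity, so a non-returner reaches no stated end of wear and no ticked adverse event assessment. Those with long exposure are the ones least often asked. If the device changes how many participants return, or how soon, the chance of having an event recorded differs between arms, and the harms comparison inherits that difference. No later analysis can recover events that were never asked about.

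**Working it through.** No sample-size or error-rate formula applies. The check is visit timing and coverage.

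**Inputs.** Minimum time in the return program: 33 days (Appendix 3). Interval from return to the 6-week visit: 6 × 7 = 42 days (section 5.2). Planned participants: 50, in two groups of 25 (section 8). Participants with extra early checks: 5 (section 5.2).

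**The 33 days.** At the stated pace of one stage every 3 days, 33 / 3 = 11 steps. The flow chart is not in the text available, so the number of steps cannot be confirmed. I take 33 days as given.

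**Timing, in days from the start of the program.**

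- First ticked adverse event assessment: day 33 at the earliest.
- 6-week visit: 33 + 42 = day 75, or 75 / 7 = 10.7 weeks, at the earliest. This assumes full activity resumes on the day of the pre-return assessment.
- Both are later for anyone who has to step back. Neither occurs for a participant who never completes the chart without pain.

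**Coverage before the pre-return visit.**

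- The first 5 enrolled are examined weekly for two weeks and then fortnightly for two fortnights: about days 7, 14, 28 and 42, with phone interviews in the first week. That is 5 / 50 = 10%.
- The other 45 / 50 = 90% have no scheduled adverse event assessment between fitting and the pre-return visit.

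**What the weekly form asks.** Appendix 2 has 13 numbered items: four on sport, pain in sport, walking and rest; five on exercise (sessions, minutes, activity, surface, exertion); two on device wear; one on other treatments; one on satisfaction. That is 4 + 5 + 2 + 1 + 1 = 13. None asks about skin, swelling or any other event.

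**Effect on the comparison.** Let a harm occur with the same probability *h* in both arms, unrelated to recovery, and let *r* be the proportion in each arm who reach the scheduled assessments. Leaving aside spontaneous reports and the first 5, the expected count from scheduled collection is 25 × *h* × *r*(device) against 25 × *h* × *r*(placebo). The ratio is *r*(device) / *r*(placebo), although the true ratio is 1. If the device helps participants return, its harms are collected more completely than those of placebo. If a harm itself prevents return, it is lost in the arm where it occurs. The direction cannot be fixed in advance, and the documents give no return rates from which to size it.

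**The case against.** The strongest reply is that section 10, Appendix 3 and the second half of section 6.1 agree with one another: a participant who worsens in rehabilitation can be seen early. On that view the 6-week sentence covers worsening after return, or is an added check, and merely lacks a time scope. Most of this stands. A reader might infer that three passages conflict with each other, or that assessment is withheld until week 6. The documents do not support either. One sentence is out of step with the rest, but it is the sentence in the safety section that deals specifically with worsening pain, and nothing in it limits it to the period after return.

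The second reply is that participants are not out of contact. The weekly form goes to the clinician from everyone, non-recoverers included, and records pain. A Medical Monitor is available. The safety committee looks at the first 5 and at anyone else who reports an adverse event. All adverse events go into a log and a case report form. So it would be wrong to infer that 45 of 50 have no scheduled safety contact, or that worsening pain goes unrecorded. What remains is narrower. The form does not ask about events other than pain, review under Appendix 3 is triggered by lack of progress and not by skin or vascular symptoms, and the other routes depend on the participant speaking up.

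A reader might also object that the first 5 could include few active-device wearers. Under simple randomisation the chance of at most one is 6/32 = 18.75%. With a fixed 25/25 split it is 369,380 / 2,118,760 = 17.4%, and with permuted blocks of 2 or 4 it is zero. Section 5.7 does not say which method applies, and section 5.3 places the skin risk in both groups, so placebo wearers are informative for that harm. The point adds nothing firm.

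**Conclusion.** The point holds in two parts. The 6-week sentence in section 6.1 cannot serve pain that worsens in rehabilitation: the visit is at day 75 or later, or never, and the sentence does not fit section 10, Appendix 3 or the paragraph that follows it. And apart from the first 5 participants, those who do not recover have no scheduled adverse event assessment, while the form that does reach them has no adverse event item.

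The consequence is under-ascertainment of harms other than shin pain in non-recoverers, possibly uneven by arm. It does not follow that the trial cannot describe device safety: returners are assessed four times, and spontaneous reports are kept for everyone.

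This rests on the 33-day minimum as stated and on counting the 6-week visit from return to full activity, as sections 2.2 and 5.2 do. If the sponsor intended to count from fitting, section 6.1 would make more sense but would contradict section 5.2, so the text needs correcting on either reading.

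**What to change.** 1. Reconcile sections 5.2, 6.1 and 10 and Appendix 3 into one consistent statement on worsening pain, including the period to which the 6-week sentence applies. Which clinical response is right is for the sponsor and investigators; none is proposed here.
2. Add one adverse event item (skin, swelling, other) to the Appendix 2 form, both weekly and fortnightly, and show it in the section 5.2 schedule from the day of fitting, so that collection no longer depends on recovery.
3. State that harms are reported by arm for all randomised participants, whether or not they return to full activity.

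The cost is some protocol wording, one more item on a form already being sent, and a little follow-up of positive answers. No extra visit is needed, and nobody has to know the allocation.
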